6. INDEPENDENT DATA MONITORING

The TNM[™] Device has been designated as a Non-Significant Risk Device for this study. However, the Sponsor has chosen to implement an IMM for the trial to provide independent safety monitoring and to confirm data integrity. The IMM is a physician with extensive experience in Parkinson's disease and clinical trials and has no perceived or real conflict of interest with the Sponsor or in the study outcomes. The IMM will review the research protocol and ongoing study activities with emphasis on data integrity, protocol adherence and study participant safety issues while making recommendations to the continuation, modification or conclusion of the trial. The IMM will review data at least four times per year during the course of the trial.

In addition to the IMM, the Sponsor will ensure critical safety and data points will be monitored per the STEM-PD Clinical Monitoring Plan (CMP) and the STEM-PD Data and Safety Management Plan (DSMP). A summary of key monitoring procedures is noted below:

Each site will be assigned a Clinical Research Associate (CRA) who will monitor the data to ensure the protection of rights and safety of human subjects, to verify the reported trial data are accurate, complete, and verifiable from source documents, and that the trial is conducted in compliance with the currently approved protocol/amendment(s), with Good Clinical Practice and with the applicable regulatory requirements. For all enrolled study participants, 100% source data review (SDR) and source data verification (SDV), where applicable, will occur of informed consent documents and process, demographics, inclusion and exclusion criteria, primary endpoint and key secondary endpoints (e.g., MDS-UPDRS Part III and CGI-I), all protocol deviations and safety reports, including adverse events and safety endpoints. Targeted source data verification, based on risk-based monitoring, will occur for all other endpoints and clinical data collected per the Targeted Source Data Verification (TSDV) portion of the CMP. Review of study-wide trends and key risk indicators (KRI) metrics will be reviewed in a departmental meeting to occur at least once a month. If trends are identified, the Sponsor will review with the study-assigned medical monitor and may implement a Correction and Preventative Action (CAPA) Plan, as necessary. The studyspecific Medical and Safety monitor, who has extensive experience with the device, will review and sign off on all AEs at least monthly, and all Unanticipated Adverse Device Effects (UADE) within 2 days of acknowledgment of the event. All UADEs will be reported to the ethics committees and all site Investigators per the protocol and regulatory requirements.

Previous studies with the Device have not reported any Serious Adverse Device Effects (SADEs) or UADEs. As none are anticipated for this study, if two or more serious and related adverse events (SADE or UADE) are reported, the study enrollment will pause while universality and unblinded review occurs by the Medical and Safety monitor. Additionally, the IMM will review these events for adjudication and agreement and will provide recommendations to the Sponsor.

7. STATISTICAL METHODS

7.1. GENERAL METHODS

Descriptive statistical methods will be used to summarize the data from this study, with formal hypothesis testing performed for the primary and key secondary efficacy endpoints. Unless stated otherwise, the term "descriptive statistics" refers to number of subjects, mean, median, standard deviation, minimum, and maximum for continuous data, and frequencies and percentages for categorical data. For categorical variables, the denominator of percentages will be the number of subjects in the treatment group, except for those collected by study visit and/or scheduled time point, in which case the denominator of percentages will be the number of subjects with a non-missing value at the visit and/or the scheduled time point.

All data collected during the study will be included in data listings. Unless otherwise noted, the data will be sorted first by treatment group, subject number, and then by date within each subject number.

All statistical testing will be two-sided and will be performed using a significance (alpha) level of 0.05 unless otherwise specified. P-values will be presented to three decimal places. For exploratory endpoints, inferential analyses including 95% confidence intervals and p-values will be provided, and no statements about statistical significance will be made. The p-values will be provided as informational only.

The statistical analyses will be conducted with the SAS® software package version 9.4 or higher. All analyses will be subject to formal verification procedures. Outputs will be reviewed by the lead statistician to ensure accuracy and consistency of analyses.

7.2. ANALYSIS POPULATIONS

Intent-to-treat Population (ITT): All randomized participants will be included in this population. This is the population that will be used for the primary analysis of efficacy and safety.

Modified Intent to treat (mITT): All eligible randomized participants who have completed at least one treatment with the study device and have completed a post-randomization assessment will be included in the mITT population. This population will be used for a secondary analysis of the primary endpoint and will be used to supplement the findings of the primary analysis.

Per-protocol Population (PP): All eligible randomized participants who (1) demonstrate at least 70% adherence of the randomized expected treatments with the Study Device³, (2) have completed the regularly scheduled end of treatment visit (day 113) (3) have not had changes to medications used to treat motor and/or non-motor symptoms of PD during the baseline or

³ Treatment data including dates and treatment durations are captured by the study device. These data files will be analyzed, and treatments lasting a minimum of 10 minutes will be considered as adherent for a given run based on flow oscillations in the Gossling Pulsatility Index after ~7 minutes of treatment Black, R., Rogers, L., Nicoletto, H., Adkins, H., Laskowitz, D. (2016). "Non-invasive neuromodulation using time-varying caloric vestibular stimulation - *abstract*." Headache **56**(S1)..

RCT, (4) have not had changes to medications that mimic motor and/or non-motor symptoms of PD during the baseline or RCT will be included in the PP population. This population will be used for a secondary analysis of the primary endpoint and will be used to supplement the findings of the primary analysis and key secondary analyses.

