7.8.2. Safety Endpoint

The change in the mini-BESTest between the end of treatment (day 113 or early withdrawal) and the baseline (day 29) will serve as an additional safety endpoint to confirm that TNM[™] treatment does not negatively impact balance, functional mobility and gait in people with PD. Mini-BESTest data collected in the OFF-state will not be included in any analysis .The largest amount by which the median change scores in the passive treatment arm can be better than the median change scores in the active treatment arm is 4 points (Godi, Franchignoni et al. 2013). Two-sided, 95% confidence intervals for the median difference in the Mini-BESTest scores for the two treatment groups will be constructed (Ganju and Rom 2017). If the confidence interval of the difference (active – passive) contains -4, then the no clinically meaningful difference between the groups exists.

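### No adherence-based analysis is clearly assigned to the 4-point mini-BESTest comparison, so dilution of balance harm in the ITT set can go unchecked

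*SAP*

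**What the plan says.** RCT SAP 7.2 defines ITT as all randomised participants and states: "This is the population that will be used for the primary analysis of efficacy and safety". The per-protocol (PP) set requires, among other things, that participants "demonstrate at least 70% adherence of the randomized expected treatments with the Study Device". Its use is described in two parts: "This population will be used for a secondary analysis of the primary endpoint", and to "supplement the findings of the primary analysis and key secondary analyses". The mini-BESTest is listed as a safety endpoint, so neither part clearly covers it.

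RCT SAP 7.8.2 takes the mini-BESTest change "between the end of treatment (day 113 or early withdrawal) and the baseline (day 29) will serve as an additional safety endpoint". It sets the margin by saying that the most by which passive median change "can be better than the median change scores in the active treatment arm is 4 points". The tool is "Two-sided, 95% confidence intervals for the median difference in the Mini-BESTest scores", and the rule is that if the interval for active minus passive "contains -4, then the no clinically meaningful difference between the groups exists". No analysis set is named there.

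Other relevant places:
- Protocol 4.2 says ITT, mITT and PP data will be analysed, without naming endpoints.
- RCT SAP 7.10.3 commits to mini-BESTest subgroups by confounding deviation: a change in PD medication, a change in symptom-mimicking medication, or an out-of-window visit while not treating as required.
- RCT SAP 7.10.6 allows an optional mini-BESTest analysis without injury-affected or off-state data.
- Protocol 6.4 says site staff will not withdraw participants for significant treatment non-adherence. Protocol 7.2.1 lists significant non-adherence to the protocol as a withdrawal criterion by investigator and sponsor decision. These two statements need reconciling.
- OLE SAP 7.3 also puts safety on an ITT set, there requiring at least one OLE treatment. OLE SAP 2.1 leaves the relation of adherence to safety to a separate plan.

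**The concern.** In a superiority test, participants who barely use the device dilute the benefit, and ITT errs on the cautious side. In a test meant to show that the device does not worsen balance by 4 points, the same participants dilute the harm, and ITT errs towards declaring safety. An early leaver with a withdrawal assessment enters the comparison with that score, however short the exposure.

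At stake is the trial's only quantitative statement on balance harm. It could be reassuring for everyone assigned to the device while people who use it as directed lose about as much balance as the plan's own margin treats as important. The device log already identifies those users.

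**Working it through.** **1. The plan's own figure.** The documents give no power or sample size for the mini-BESTest. The sizing figure in RCT SAP 4 is 89.2% power for 2.64 points on MDS-UPDRS Part I, with SD 5.32, 83 per arm and two-sided 0.05. Standard error = 5.32 × √(2/83) = 0.826. Then 2.64/0.826 − 1.96 = 1.24, and Φ(1.24) = 89.2%. It reproduces, but here it supplies only the 83 per arm.

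**2. Inputs for balance.** From the documents: margin 4 points, two-sided 95% interval, 83 completers per arm. Assumed, because the documents do not say: SD of mini-BESTest change 3 to 5; no change in the passive arm; users of the active device lose exactly 4 points; a share f of the active arm has no exposure effect.

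**3. Dilution of the mean.** ITT mean loss = 4 × (1 − f). The users' loss that leaves the ITT mean exactly on the margin is 4/(1 − f).

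**4. Chance of a false no-harm conclusion under a conventional rule** (lower 95% limit above -4). Two intervals were used, because 7.8.2 does not say how the median difference is estimated.
- Difference of sample medians: m is the median of the normal mixture in the active arm, SE is the asymptotic standard error, and the chance is Φ((m + 4)/SE − 1.96). Example with SD 4, f = 10%: m = −3.64 and SE = 1.56/1.96 = 0.796, so Φ(0.36/0.796 − 1.96) = Φ(−1.51), about 6.5%.
- Hodges-Lehmann shift: repeated simulations, with 1,500 or 2,000 trials per cell where the count was recorded.

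| Unexposed share f | ITT mean loss | Users' loss at which ITT mean is 4 | False no-harm, medians | False no-harm, Hodges-Lehmann |
|---|---|---|---|---|
| 0% | 4.0 | 4.00 | 2.5% | about 2-3% |
| 10% | 3.6 | 4.44 | 5.7-7.8% | about 6-12% |
| 20% | 3.2 | 5.00 | 11.5-19.9% | about 15-30% |
| 30% | 2.8 | 5.71 | 21.1-40.3% | about 29-61% |

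Ranges run over SD 5 to SD 3. With 92 per arm (half of the 184 randomised) the median-based figures barely move: 5.9-8.2% at f = 10% and 12.3-21.5% at f = 20%.

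**5. The rule as written** (interval contains -4), median-based, 83 per arm:
- True loss 4 points, no dilution: no meaningful difference is declared 95% of the time.
- True loss 5 points: 60-82%.
- No true difference: 0-1.6%.
- Users lose 4 points, f = 10%: about 92-93%.

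Under this wording dilution lowers the false no-harm rate at a 4-point loss, so the table in step 4 applies only once the rule is corrected.

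**6. Effect of the added condition.** When the adherent set must pass too, the simulated false no-harm rate returned to 2.1-3.4% in every cell, assuming that users are correctly identified and not self-selected. If there is truly no harm and 70% of each arm is adherent (0.7 × 83 = 58), the adherent set passes at least 98% of the time with the Hodges-Lehmann interval. With the difference of medians at SD 5, SE = 1.2533 × 5 × √(2/58) = 1.16, and Φ(4/1.16 − 1.96) is about 93%.

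**The case against.** **The rule as written reverses the argument.** The figures in step 4 use a rule that 7.8.2 does not contain. This stands: the decision rule is the larger defect on the page, and the dilution figures depend on its correction. Correcting the rule alone would still leave the dilution.

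**ITT is not the only balance analysis.** A reader might infer that it is. The documents do not support that: 7.10.3 and 7.10.6 add mini-BESTest analyses, Protocol 4.2 promises PP data without restriction, and the PP wording ("supplement the findings of the primary analysis and key secondary analyses") could be read to cover the primary safety analysis. OLE SAP 7.3 also provides an mITT analysis for endpoints with scheduled post-treatment data. What remains is that none of these clearly applies an adherence threshold to the RCT balance comparison. Exploratory appendices that are not available here may relate adherence to safety, but nothing in 7.8.2 links its conclusion to them.

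**Early leavers do not all count as treated.** They enter only if assessed at withdrawal. No imputation is specified for the mini-BESTest, so the others drop out. Early-withdrawal scores may also retain people who stopped because of imbalance, whereas the calculation gives every unexposed participant zero harm.

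**The shares are assumed.** A reader might take the planned 10% attrition as a non-use rate. It is not one, and the 83 per arm are already net of it. Protocol 2.2.2 describes adherence in earlier trials as excellent. All of this stands.

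**The adherent set is self-selected.** This also stands, and is why it should supplement ITT and not replace it.

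**Conclusion.** The point holds as a gap in assignment: ITT is the primary safety set, and neither 7.2 nor 7.8.2 clearly ties an adherence-based analysis to a margin comparison for which ITT dilution is anti-conservative.

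It would go too far to infer that harm is in fact hidden below the margin. That depends on the users' loss, the non-use share and the SD. With 10% unexposed, the ITT mean falls inside the margin only for a users' loss between 4 and 4.44 points, and a much larger loss would still show. Under a corrected rule, with SD 3 to 5 and a users' loss of exactly 4 points, false no-harm is about 6-12% with 10% unexposed and about 12-30% with 20%, taking both interval types together, against a nominal 2.5%. This should be fixed; confidence in its size is moderate, because every input beyond the margin, the interval level and the sample size is assumed.

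**What to change.** 1. In RCT SAP 7.8.2, correct the rule first: conclude no clinically meaningful difference only if the lower 95% limit of active minus passive lies above -4. State how the median difference and its interval are estimated.
2. Keep ITT as the main set. Add the same comparison in participants of both arms with at least 70% logged adherence (the first PP criterion) and a day-113 score. Draw the no-harm conclusion only if both intervals exclude a 4-point disadvantage.
3. Name this use of the adherent set in 7.2.
4. Mirror it in OLE SAP 7.3 and 7.9.2, with adherence from the first OLE treatment period and a day-197 score. The score condition matters there, because OLE SAP 7.4 divides use by days participated, so an early leaver can count as adherent. Section 7.9.2 should also state the direction of its difference, since it compares an upper limit with 4.

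The cost is SAP wording and one more run on adherence data already derived for PP. The added set is smaller and selected after randomisation, so its interval is wider and its comparison is not protected by randomisation. As an extra condition beside the corrected ITT test, it can only make the no-harm claim stricter.

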7.3. DEFINITIONS

Study day: The study day will be calculated in reference to the date of the first baseline virtual visit (Day 0) of the study.

Baseline value: Where multiple data points are collected during the baseline period, the baseline value for each participant will be calculated as the mean of assessments taken during the baseline period excluding the screening value unless otherwise noted. Exceptions to this will be for the following outcomes:

- PRO-PD where the baseline value is defined as the second data collection (i.e., first data collection will be discarded), if both are available, otherwise the first data point will be used (this value could be the Screening value). The scale's author indicated that scores from the first completion of the assessment have higher variability relative to the scores from subsequent administrations.
- the MDS-UPDRS III where the baseline value is defined as the second data collection (i.e., the in-clinic assessment). However, if the end of treatment visit is collected virtually due to the inability of the participant to attend the in-clinic visit, the data from the first virtual baseline assessment, appropriately prorated, will serve as the baseline for that participant.

To be considered baseline data, data must be collected prior to or on the day of first treatment with the study Device.

Duration of Follow-up: The duration of follow-up will be defined as the number of days from Baseline Visit 1 until the End of Study assessment or the last completed visit (phone call, virtual or in clinic).

Adverse Event:

Per protocol, an AE is any untoward medical occurrence, unintended disease or injury, or untoward clinical signs (including abnormal laboratory findings) in participants, users, or other persons, whether or not related to the investigational medical device. This definition includes events related to the investigational medical device and the events related to the procedures involved. For purposes of analyses, any AE specified on the Adverse Events eCRF page is considered an AE.

Adverse Device Effect (ADE):

Per protocol, an ADE is an AE related to the use of an investigational medical device. For purposes of analysis, any AE specified on the Adverse Events eCRF page that is possibly related, probably related, or related to the study device will be considered an ADE.

Serious Adverse Event (SAE):

Per protocol, a SAE is an AE that has

- Led to death,
- Led to serious deterioration in the health of the participant, that either resulted in:
 - 1. A life-threatening illness or injury, or
 - 2. A permanent impairment of a body structure or a body function, or
 - 3. In-patient or prolonged hospitalization, or
 - 4. Medical or surgical intervention to prevent life-threatening illness or injury or permanent impairment to a body structure or body function.
- Led to fetal distress, fetal death or congenital abnormality or birth defect.

For analysis purposes, SAEs are AEs which are defined as serious on the Adverse Events eCRF (page 103).

Serious Adverse Device Effect (SADE):

Per protocol, a SADE is an ADE that has resulted in any of the consequences characteristic of a serious adverse event. For analysis purposes, any AE on the Adverse Events eCRF page that is possibly related, probably related, or related to the study device and is noted as serious will be considered a SADE.

Unexpected Adverse Device Effect (UADE):

Per protocol, a UADE is an SADE on health or safety or any life-threatening problem or death caused by, or associated with, a device, if that effect problem, or death was not previously identified in nature, severity, or degree of incidence in the investigational plan or application (including a supplementary plan or application), or any other unanticipated serious problem associated with a device that relates to the rights, safety, or welfare of participants. For analysis purposes, any event noted on the SADE/UADE Report eCRF page that is noted as a UADE will be considered a UADE.

SADEs and UADEs are AEs specified as such on page 111 of the eCRF. More information on SAEs, ADEs, SADEs, and UADEs can be found in Protocol (Version 6.0: 02 Apr 2024) Section 8.2.

7.4. ANALYSIS OF STUDY CONDUCT

The number of participants screened and the number of those randomized falling into the ITT, mITT and PP populations will be summarized.

Study treatment administration, duration of follow-up, discontinuation from study treatment and the reasons for discontinuation will be summarized by treatment group for all randomized participants. Coded protocol deviations and protocol violations will also be summarized as follows:

• Major/Important versus Minor versus No Impact, where:

- Major/Important are protocol deviations that might significantly impact completeness, accuracy, and/or reliability of study data OR could significantly affect a participant's rights, safety or well-being
- Minor are protocol deviations with minor impact on data quality or patient safety
- No impact are protocol deviations that do not impact data quality or patient safety
- Specific subcategories of coded deviations and violations will be further summarized by treatment group.

7.5. DESCRIPTION OF THE DATASET USED FOR ANALYSIS

SAS-compatible data sets will be exported directly from the iMediData RAVE Electronic Data Capture platform. Exceptions may include data for the MDS-UPDRS Part III that has been scored by central blinded raters within the Machine Medicine Kelvin-PD platform, data related to Finger-tapping tests and Timed Up and Go tests captured with the Mon4t EncephaLog application, treatment adherence data downloaded from the returned study Devices, a file that defines types of medications taken to address motor and nonmotor symptoms of PD including the levodopa equivalent daily dose for each randomized participant, the list of centers that required inclusion of the Sponsor name on the informed consent forms, and a file that defines all the assignment of each consented participant into populations for analysis (e.g., ITT, mITT and PP) and reasons for exclusion and withdrawal where appropriate. Data for these exceptions will be provided as csv files created with Microsoft Excel.

7.6. ANALYSIS OF TREATMENT GROUP COMPARABILITY

An evaluation of treatment group characteristics will be compared across the two treatment arms. The characteristics will include demographics, baseline disease characteristics, concomitant medications, scores in outcome measures at baseline. Descriptive statistics will be presented by treatment groups. Differences in baseline scores will be determined using parametric or non-parametric approaches as appropriate based upon visual inspection of the distribution. Categorical variables will be summarized using frequencies and percentages. Baselines will be considered different in circumstances where p < 0.05. Numbers of early withdrawals will be compared across treatment arms using Fisher's exact test. Reasons provided for early post-randomization withdrawals will be reported. Withdrawals due to similar adverse events will be grouped into categories. Fisher's exact tests stratified by category will then be conducted to determine if there is an association between the number of subjects experiencing withdrawal due to adverse events and treatment arm.

